6.2.1 Dosage, Administration, and Schedule

6.2.1.1 Screening

During screening, subjects will undergo SC placebo injection with the device to be used during the study (AMD or Al/pen). Subjects must tolerate the placebo injection prior to randomization.

6.2.1.2 Double-blind Treatment Period

The IP (420 mg evolocumab or matching placebo via AMD, or Al/pen) will be administered QM on day 1, week 4, week 8, week 12, week 16, and week 20.

SC evolocumab and placebo will be administered at the study site or in an appropriate non-clinic setting (eg, at the subject's home). Observed, in-clinic dosing should occur at day 1 and week 20. Subjects who do not wish to self-inject at home may return to the clinic for injection. See Table 3 for the schedule of in-clinic visits.

The IP will be administered SC in accordance with instructions in the IPIM and the Information for Use (IFU). The subject (or designee, if not a qualified healthcare professional) must have demonstrated competency, as per site judgment, at administration of SC injections before self-administration is permitted: the first

Protocol Number: 20130286

Page 25 of 73 Date: 30 January 2017

self-administered dose by the subject (or designee, if not a healthcare professional) must be administered at the site under the supervision of a healthcare provider. If IP is to be administered during the study visit, administration must occur after all other procedures have been completed.

When IP is mandated to be administered at the study site, the date and time of administration, the body location of the injection, and whether the injection was administered fully, partially, or not at all, in addition to the reason for a partial/lack of injection, are to be provided. When IP can be administered at an appropriate non-clinic setting (eg, at the subject's home), at a minimum, the dates the devices were dispensed and returned, the number of devices dispensed and returned, and number of devices administered fully, partially, or not at all, in addition to the reason for a partial/lack of injection, must be provided.

When IP is mandated to be administered at the study site, the date and completion time of administration, the body location of the injection, and whether the injection was administered fully, or partially, or not at all administered, in addition to the reason for a partial/lack of injection, are to be recorded on each subject's CRF provided. When IP can be administered at an appropriate non-clinic setting (eg, at the subject's home), a non-investigator site location, at a minimum, the dates that the devices were dispensed and the used devices were returned, the number of devices dispensed and returned, and number of devices administered fully, partially, or not at all, in addition to the reason for a partial/lack of injection, must be provided whether each device was returned fully or partially used are to be recorded on each subject's CRF.

Overdose with this product has not been reported.

6.2.1.3 **Open-label Period**

Product: Evolocumab

Subjects who receive a dose of IP at week 20 will continue in an open-label period. During the open-label period, all subjects will be treated with 420 mg evolocumab via AMD, or Al/pen. Dosing at week 24 is expected to be in-clinic while dosing for weeks 28, 32, 36, 40, 44, and 48 is expected to be in an appropriate non-clinic setting (eg, at the subject's home, even on weeks with in-clinic visits); however, subjects who do not wish to self-inject at home may return to the clinic for injection.

Protocol Number: 20130286

Date: 30 January 2017

Page 26 of 73

6.2.2 Dosage Adjustments, Delays, Rules for Withholding or Restarting,

No dose adjustments are allowed in this study. If, in the opinion of the investigator, a subject is unable to tolerate a specific dose of IP, that subject will discontinue IP but will continue to return for all other study procedures and measurements until the EOS visit.

If a dose of evolocumab is missed, administration should occur as soon as possible if there are > 7 days until the next scheduled dose. If there are less than 7 days before the next scheduled dose, the missed dose should be omitted and the next dose should be administered according to the original schedule.

6.3 Hepatotoxicity Stopping and Rechallenge Rules

Permanent Discontinuation

Subjects with abnormal hepatic laboratory values (ie, alkaline phosphatase [ALP], AST, ALT, total bilirubin [TBL]) **and/or international normalized ratio (INR)** and/or signs/symptoms of hepatitis (as described below) may meet the criteria for withholding or permanent discontinuation of Amgen IP or other protocol-required therapies as specified in the Guidance for Industry Drug-Induced Liver Injury (DILI): Premarketing Clinical Evaluation (July 2009).

6.3.1 Criteria for Withholding and/or Permanent Discontinuation of Amgen Investigational Product and Other Protocol-required Therapies Due to Potential Hepatotoxicity

The following stopping and/or withholding rules (Table 1) apply to subjects for whom another cause of their changes in liver biomarkers (TBL, INR and transaminases) has not been identified.

Important alternative causes for elevated AST/ALT and/or TBL values include, but are not limited to:

Hepatobiliary tract disease

Product: Evolocumab

- Viral hepatitis (eg, Hepatitis A/B/C/D/E, Epstein-Barr virus, cytomegalovirus, herpes simplex virus, varicella, toxoplasmosis, and Parvovirus)
- Right-sided heart failure, hypotension or any cause of hypoxia to the liver causing ischemia
- Exposure to hepatotoxic agents/drugs or hepatotoxins, including herbal and dietary supplements, plants, and mushrooms
- Heritable disorders causing impaired glucuronidation (eg, Gilbert's syndrome, Crigler-Najjar syndrome) and drugs that inhibit bilirubin glucuronidation (eg, indinavir, atazanavir)
- Alpha-one antitrypsin deficiency
- Alcoholic hepatitis

Product: Evolocumab
Protocol Number: 20130286
Date: 30 January 2017
Page 27 of 73

- Autoimmune hepatitis
- Wilson's disease and hemochromatosis
- Nonalcoholic fatty liver disease including steatohepatitis
- Nonhepatic causes (eg, rhabdomylosis, hemolysis)

Amgen IP (evolocumab/placebo) and other protocol-required therapies should be discontinued permanently and the subject should be followed according to the recommendations in Appendix A (Additional Safety Assessment Information) for possible DILI.

Rechallenge may be considered if an alternative cause for impaired liver tests (ALT, AST, ALP) and/or elevated TBL, is discovered and the laboratory abnormalities resolve to normal or baseline (Section 6.3.2).

Table 1. Conditions for Withholding and/or Permanent Discontinuation of Amgen Investigational Product and Other Protocol-required Therapies Due to Potential Hepatotoxicity

Analyte	Temporary Withholding	Permanent Discontinuation
Total bilirubin	> 3x ULN at any time	> 2x ULN
		OR
INR		> 1.5 (for subjects not on anticoagulation therapy)
	OR	AND
AST/ALT	> 8x ULN at any time > 5x ULN but < 8x ULN for ≥ 2 weeks	In the presence of no important alternative causes for elevated AST/ALT and/or total bilirubin values
	> 5x ULN but < 8x ULN and unable to adhere to enhanced monitoring schedule	> 3x ULN (when baseline was < ULN)
	> 3x ULN with clinical signs or symptoms that are consistent with hepatitis (such as right upper quadrant pain/tenderness, fever, nausea, vomiting, jaundice)	
	OR	
ALP	> 8x ULN at any time	

ALP=alkaline phosphatase; ALT=alanine aminotransferase; AST=aspartate aminotransferase; INR=international normalized ratio; ULN=upper limit of normal.

Protocol Number: 20130286

Date: 30 January 2017

Page 28 of 73

6.3.2 Criteria for Rechallenge of Amgen Investigational Product and Other Protocol-required Therapies After Potential Hepatotoxicity

The decision to rechallenge the subject should be discussed and agreed upon unanimously by the subject, investigator, and Amgen.

If signs or symptoms recur with rechallenge, then evolocumab/placebo should be permanently discontinued. Subjects who clearly meet the criteria for permanent discontinuation (as described in Section 6.3.1) should never be rechallenged.

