6.4 Other Protocol-required Therapies

Other protocol-required therapies are stable HIV therapy and stable dose of lipid-lowering therapy, if applicable, as defined in subject eligibility (Section 4.1).

Other protocol-required therapies are not provided or reimbursed by Amgen (except if required by local regulation). The investigator will be responsible for obtaining commercially available supplies of these protocol-required therapies.

Additional details regarding these protocol-required therapies are provided in the IPIM.

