8. WITHDRAWAL FROM TREATMENT, PROCEDURES, AND STUDY

8.1 **Subjects' Decision to Withdraw**

Subjects have the right to withdraw from the study at any time and for any reason without prejudice to their future medical care by the physician or at the institution.

Subjects (or a legally acceptable representative) can decline to continue receiving IP and/or other protocol-required therapies or procedures at any time during the study but continue participation in the study. If this occurs, the investigator is to discuss with the subject the appropriate processes for discontinuation from IP or other protocol-required therapies and must discuss with the subject the options for continuation of the Schedule of Assessments (Table 3) and collection of data, including endpoints and adverse events. The investigator must document the change to the Schedule of Assessments (Table 3) and the level of follow-up that is agreed to by the subject (eg, in person, by

Protocol Number: 20130286

Date: 30 January 2017

Page 44 of 73

telephone/mail, through family/friends, in correspondence/communication with other physicians, from review of the medical records).

Withdrawal of consent for a study means that the subject does not wish to receive further protocol-required therapies or procedures, and the subject does not wish to or is unable to continue further study participation. Subject data up to withdrawal of consent will be included in the analysis of the study, and where permitted, publicly available data can be included after withdrawal of consent. The investigator is to discuss with the subject appropriate procedures for withdrawal from the study.

8.2 Investigator or Sponsor Decision to Withdraw or Terminate Subjects' Participation Prior to Study Completion

The investigator and/or sponsor can decide to withdraw a subject(s) from IP and/or other protocol-required therapies, protocol procedures, or the study as a whole at any time prior to study completion.

Subjects may be eligible for continued treatment with Amgen IP and/or other protocol-required therapies by a separate protocol or as provided for by the local country's regulatory mechanism, based on parameters consistent with Section 12.1.

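### Read with Protocol 6.4, the liver stopping rule in Protocol 6.3.1 would permanently stop HIV therapy after an unexplained event, because no liver passage exempts antiretrovirals

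*Protocol*

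**What the plan says.** Protocol 6.3.1 first sets the scope of the liver rules. They "apply to subjects for whom another cause of their changes in liver biomarkers (TBL, INR and transaminases) has not been identified". It then lists alternative causes, refers to Table 1 for the triggers, and gives the operative instruction: "Amgen IP (evolocumab/placebo) and other protocol-required therapies should be discontinued permanently", with follow-up under Appendix A.

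Protocol 6.4 supplies the definition: "Other protocol-required therapies are stable HIV therapy and stable dose of lipid-lowering therapy, if applicable, as defined in subject eligibility". It adds that "Additional details regarding these protocol-required therapies are provided in the IPIM".

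Two other lines in the liver text describe the scope differently. The lead-in to 6.3 says that subjects with abnormal liver values "may meet the criteria for withholding or permanent discontinuation of Amgen IP or other protocol-required therapies". Section 6.3.2 says: "If signs or symptoms recur with rechallenge, then evolocumab/placebo should be permanently discontinued".

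Section 6.3.1 also allows rechallenge to be considered if an alternative cause is found and the laboratory values return to normal or baseline. Section 6.3.2 rules out rechallenge for subjects who clearly meet the permanent criteria.

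**The concern.** Inclusion criterion 103 requires stable HIV therapy, and criterion 105 requires a viral load of 50 copies/mL or less at screening. Every subject therefore enters on a suppressive regimen, and that regimen falls within the 6.4 definition. The stopping sentence in 6.3.1 joins it to the investigational product with 'and'.

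Two things are at stake. The first is patient safety: a literal reading permanently stops effective antiretroviral therapy in a subject whose liver event has not been attributed to it. The protocol's own background (Section 2.1) cites a treatment-interruption study in which cardiovascular events were more frequent after antiretrovirals were stopped, with a hazard ratio of 1.57. That setting differs from a liver stopping rule, so the figure is not used here to size any harm. It does show that the sponsor regards stopping antiretrovirals as consequential. The second is consistent conduct: one site could follow the 'and' and another the 'or', and each could point to protocol text.

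**Working it through.** No arithmetic applies. The check is whether the liver text, taken together, reaches HIV therapy and whether anything takes it back out.

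1. **Trigger.** The operative sentence in 6.3.1 does not state its own trigger. The permanent column of Table 1 is the natural one: total bilirubin > 2x ULN or INR > 1.5 (in subjects not on anticoagulation), together with AST/ALT > 3x ULN from a baseline below ULN, and no important alternative cause.

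2. **What is stopped.** Substituting the 6.4 definition into 6.3.1, the sentence covers evolocumab/placebo, HIV therapy and lipid-lowering therapy. One verb governs all three.

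3. **When the background regimen is caught.** Hepatotoxic drugs are a listed alternative cause, and indinavir and atazanavir are named as drugs that impair bilirubin glucuronidation. An event attributed to an antiretroviral therefore falls outside the rule. The rule applies when the antiretroviral has not been identified as the cause, so the regimen it stops is one not shown to be at fault.

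4. **Search for an exemption.** None appears in 6.3, 6.3.1, Table 1, 6.3.2 or Appendix A. Section 9.1.2.1 leaves management of HIV infection and other concomitant illness to clinical judgment, but it does so under the heading of worsening HIV disease. It does not mention the liver rules.

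5. **Consistency within the liver text.**
   - 6.3 lead-in: product 'or' other therapies.
   - 6.3.1 operative sentence: product 'and' other therapies, to be stopped.
   - 6.3.2 on recurrence after rechallenge: evolocumab/placebo only.
   - Appendix A, minimum observation: 4 weeks counted from stopping all product 'and' protocol-required therapies.

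   The headings of 6.3.1 and 6.3.2 and the Table 1 title also say 'and', but they only mark subject matter. The lead-in and the recurrence line leave it unclear whether the sponsor meant the 6.3.1 sentence to reach background therapy.

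6. **Consequence for follow-up.** If HIV therapy is continued, the 4-week minimum in Appendix A has no clear starting date, because it is counted from the stopping of everything.

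**The case against.** The strongest reply is that the text is softer and narrower than a literal reading suggests. Most of this stands and limits the point:

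- The verb is 'should'.
- The rule covers only unexplained events.
- Rechallenge may be considered if another cause emerges and values resolve. The permanent criteria themselves require no important alternative cause, so a later finding can reopen treatment.
- Section 6.5 lets the investigator prescribe other medication for supportive care, and 6.8 does not bar antiretrovirals, so a replacement regimen remains possible.
- Section 6.4 refers to the Investigational Product Instruction Manual, which was not available and may contain an exemption.

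None of this supplies an exemption in the protocol, where a site would look for the stopping rule.

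A reader might infer several stronger points that the documents do not support:

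- **That the protocol contradicts itself widely.** Section 8.1 says that subjects "can decline to continue receiving IP and/or other protocol-required therapies or procedures at any time during the study", and 8.2 says: "The investigator and/or sponsor can decide to withdraw a subject(s) from IP and/or other protocol-required therapies". These are general withdrawal provisions, and 9.1.2 is the general adverse-event rule. None conflicts with a specific liver rule. Nor do the two 'or' lines in Appendix A, which set who is followed and when testing may be spaced out. An inclusive 'or' there fits a rule that stops both.
- **That any Table 1 event ends HIV therapy permanently.** Table 1 separates temporary withholding from permanent discontinuation, so the narrower trigger is the natural one.
- **That close observation has no start.** It begins when product or protocol-required therapy is withheld and runs until values recover. Only the 4-week minimum is ambiguous.
- **That lipid-lowering drugs should be exempted too.** The harm argued concerns antiretrovirals. Dropping the mandatory stop for statins would remove a safeguard against possibly hepatotoxic drugs.

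**Conclusion.** The concern holds as a minor defect of wording. As written, 6.3.1 with 6.4 directs permanent discontinuation of HIV therapy for an unexplained liver event meeting the permanent criteria. No liver passage exempts antiretrovirals, and two lines in the same text leave the intent uncertain.

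Few subjects should be affected. The documents give no expected number meeting Table 1, and none is assumed. No size of harm and no effect on the LDL-C result are claimed. The conclusion rests on two assumptions: that the operative sentence is tied to the permanent column of Table 1, and that the instruction manual does not already exempt HIV therapy. If the manual does, the remaining task is to bring that exemption into the protocol.

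**What to change.** In 6.3.1, Table 1, 6.3.2 and Appendix A, exempt HIV therapy from mandatory withholding, permanent discontinuation and the bar on rechallenge by adding:

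*HIV therapy is continued, switched or interrupted at the investigator's judgment in consultation with the medical monitor; the change and its reason are recorded.*

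Keep the existing rule for evolocumab/placebo and for lipid-lowering therapy. In Appendix A, count the minimum 4-week observation from the last dose of investigational product or of any background drug stopped for the event.

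The cost is a clarification letter or a wording amendment. Visits and sample size do not change, and Section 7.3.6 already collects the reason for any change to HIV therapy. The downside is that an antiretroviral that may be hepatotoxic is no longer stopped automatically, though the investigator can still stop it.

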Appendix A. Additional Safety Assessment Information

Adverse Event Grading Scale

Refer to the NCI Common Terminology Criteria for Adverse Events (CTCAE) Version 4.0. The CTCAE is available at the following link:

http://ctep.cancer.gov/protocolDevelopment/electronic applications/ctc.htm

Drug-induced Liver Injury Reporting & Additional Assessments Reporting

To facilitate appropriate monitoring for signals of DILI, cases of concurrent AST or ALT and TBL according to the criteria specified in Section 6.3 require the following:

- The event is to be reported to Amgen as a serious adverse event within 24 hours of discovery or notification of the event (ie, before additional etiologic investigations have been concluded)
- The appropriate CRF (eg, Event CRF) that captures information necessary to facilitate the evaluation of treatment-emergent liver abnormalities is to be completed and sent to the Amgen.

Other events of hepatotoxicity and potential DILI are to be reported as serious adverse events if they meet the criteria for a serious adverse event defined in Section 9.2.2.2.

Additional Clinical Assessments and Observation

All subjects in whom IP or protocol-required therapies is/are withheld (either permanently or conditionally) due to potential DILI as specified in Sections 6.3.1 and 6.3.2 or are to undergo a period of "close observation" until abnormalities return to normal or to the subject's baseline levels. Assessments that are to be performed during this period include:

- AST, ALT, ALP, and bilirubin (total and direct) is to be repeated within 24 hours
- In cases of TBL > 2x ULN, retesting of liver tests, and bilirubin (total and direct) is to be performed every 24 hours until laboratory abnormalities improve

Product: Evolocumab
Protocol Number: 20130286

Date: 30 January 2017 Page 68 of 73

Testing frequency of the above laboratory tests may decrease if the abnormalities stabilize or the IP or protocol-required therapies has/have been discontinued AND the subject is asymptomatic.

- Initiate investigation of alternative causes for elevated AST or ALT and/or elevated TBL:
 - Obtain complete blood count with differential to assess for eosinophilia
 - Obtain serum total immunoglobulin IgG, Anti-nuclear antibody (ANA), Anti Smooth Muscle Antibody, and Liver Kidney Microsomal antibody 1 (LKM1) to assess for autoimmune hepatitis
 - Obtain serum acetaminophen (paracetamol) levels
 - Obtain a more detailed history of:

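### Minor, wrong as written: the permanent-stop sentence in Protocol 6.3.1 is not limited to Table 1's Permanent Discontinuation column, so it contradicts the table for subjects who meet only the Temporary Withholding column

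*Protocol*

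**What the plan says.** Protocol 6.3 opens by saying that subjects with abnormal liver values "may meet the criteria for withholding or permanent discontinuation of Amgen IP or other protocol-required therapies", which names two outcomes. Section 6.3.1 then sets the scope: "The following stopping and/or withholding rules (Table 1) apply to subjects for whom another cause of their changes in liver biomarkers" (TBL, INR and transaminases are named) has not been found. A list of alternative causes follows, and then the instruction that "Amgen IP (evolocumab/placebo) and other protocol-required therapies should be discontinued permanently", with follow-up under Appendix A. The next sentence is about restarting: "Rechallenge may be considered if an alternative cause for impaired liver tests (ALT, AST, ALP) and/or elevated TBL, is discovered" and the values have returned to normal or baseline.

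Table 1 gives the criteria in two columns. The Temporary Withholding column includes, in its AST/ALT row, "> 8x ULN at any time", with no bilirubin or INR requirement. The Permanent Discontinuation column requires TBL above 2x ULN or INR above 1.5 (in subjects not on anticoagulants), together with AST/ALT above 3x ULN from a baseline below ULN, and no important alternative cause.

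Two other places refer back to these rules. Section 6.3.2 says "Subjects who clearly meet the criteria for permanent discontinuation (as described in Section 6.3.1) should never be rechallenged". Appendix A prescribes close observation for all subjects in whom treatment is "withheld (either permanently or conditionally) due to potential DILI as specified in Sections 6.3.1 and 6.3.2".

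**The concern.** The permanent-stop sentence is an operative safety instruction that names neither a column nor a threshold. Its only condition is the one in the lead-in, that no other cause has been identified. Table 1 applies under the same condition, yet sends some results only to a temporary hold. For those results the protocol gives two different actions.

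What is at stake is consistent handling across about 75 sites (Protocol 3.2). One site could record a permanent stop where another records a hold for the same result. The label can reach the analysis in two places. SAP 7.2 defines non-adherence for the completer set by the reason and date for ending IP, and SAP 10.6.1 tabulates adverse events leading to withdrawal of IP.

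**Working it through.** The plan gives no figure to reproduce. The check applies Table 1 to example subjects and compares the result with the sentence.

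**Criteria, from Table 1 (multiples of ULN, except INR)**

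- Temporary, met by any one of several criteria. Two are used here: AST/ALT > 8, or TBL > 3.
- Permanent: (TBL > 2 or INR > 1.5) and AST/ALT > 3 with baseline below ULN and no important alternative cause.

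**Example 1.** ALT 9, TBL 2, INR 1.5, baseline ALT below ULN, no other cause identified. These are the highest TBL and INR values that still stay out of the permanent column.

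- Temporary: 9 > 8 is true, so the column is met.
- Permanent: (2 > 2 is false, or 1.5 > 1.5 is false) and (9 > 3 is true) gives false, so the column is not met.

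**Example 2.** TBL above 3, AST/ALT not above 3, no other cause identified.

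- Temporary: the TBL criterion is met.
- Permanent: the bilirubin condition is true but the AST/ALT condition is false, so the column is not met.

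**Control.** ALT 9, TBL above 2, baseline ALT below ULN, no other cause identified. The permanent column is met.

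| Subject | Action under Table 1 | Action under the 6.3.1 sentence |
|---|---|---|
| Example 1 | Withhold temporarily | Stop permanently |
| Example 2 | Withhold temporarily | Stop permanently |
| Control | Stop permanently | Stop permanently |

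The text and table agree for subjects in the permanent column and disagree for those who meet only the temporary column. The second group is not empty.

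It can also include subjects whose AST/ALT was not below ULN at baseline, because they cannot satisfy the permanent AST/ALT criterion at all. Such subjects can enrol: exclusion criterion 209 allows stable chronic hepatitis C with AST and ALT below 5x ULN. If hepatitis C is judged to be the cause, the 6.3.1 rules do not apply. If it is not, the same conflict arises.

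The examples use transaminases and bilirubin on purpose. ALP has its own row in the temporary column, but the lead-in condition does not name ALP, so an ALP-only example would be weaker.

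**Is the limit stated elsewhere?** The opening of 6.3, the Table 1 headings and Appendix A all treat a non-permanent hold as a real outcome. That shows the intent, but none of them attaches a limit to the sentence.

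**The case against.** The strongest defence is that context already supplies the limit. The section title, the lead-in and the table all distinguish holding from stopping, and a site acting on the sentence alone would have to ignore half of the table it belongs to. This stands as a reason to rate the point minor. It does not remove the contradiction in an instruction that sites are expected to follow.

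A second defence reads the text as a sequence: hold, investigate, and make the stop permanent if no cause is found. The restart sentence comes straight after and ties a return to IP to finding a cause, so this reading is plausible. But it is not stated, and it would make a stop permanent without the laboratory thresholds that the permanent column requires.

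A reader might also infer more than the documents support:

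- **That rechallenge is barred for temporary-only subjects.** Section 6.3.2 bars it for those who clearly meet the permanent criteria. The disputed sentence states an action, and the only permanent criteria in 6.3.1 are those in the permanent column. Rechallenge also needs the agreement of subject, investigator and sponsor, so it is not left to each site.
- **That the doses remaining after an abnormal result are lost because of this sentence.** The only restart route stated in 6.3 needs an alternative cause and resolved values. If no cause is found, that route is closed under either reading. If one is found, it is open under either reading. Open-label entry requires the week 20 dose (Protocol 6.2.1.3), so a temporary hold spanning week 20 would forfeit it too.
- **That the primary result is threatened.** SAP 10.5.1.1 uses all observed LDL-C values whether or not the subject stayed on IP, and Protocol 6.2.2 keeps subjects who cannot tolerate IP in follow-up.

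**Conclusion.** The point holds as a minor error in the current wording. For a subject who meets only the Temporary Withholding column, the 6.3.1 sentence and Table 1 prescribe different actions. This rests on reading the sentence literally under the lead-in condition, and on reading the permanent column as a conjunction, as its layout indicates.

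The size is small. The number of subjects affected cannot be derived from the documents, and the intent is recoverable. The effect on the primary analysis is limited. What remains is possible inconsistency in the initial hold-or-stop decision and in how it is recorded. No figure for lost doses and no extended rechallenge bar should be attached to it.

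A separate, secondary question concerns background treatment. Section 6.4 states that "Other protocol-required therapies are stable HIV therapy and stable dose of lipid-lowering therapy", where applicable. Taken literally, the sentence therefore also ends HIV and lipid-lowering therapy for good. The Table 1 title names these therapies too, so inclusion may be intended. Only the sponsor can say, and this question adds no weight to the main point.

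**What to change.** 1. Begin the sentence in 6.3.1 with a limiting clause: *For subjects who meet the Permanent Discontinuation criteria in Table 1,* and leave the rest as it stands.
2. Add one sentence: *Subjects who meet only the Temporary Withholding criteria in Table 1 have IP withheld.* No follow-up text is needed, because Appendix A already covers conditionally withheld subjects.
3. As a separate item, have the sponsor confirm whether background HIV and lipid-lowering therapy (Section 6.4) are meant to be included in the stop.

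No new restart rule is proposed; that is a clinical decision for the sponsor. The cost is one clause, one sentence and one confirmation, in an amendment or clarification letter. No visits, tests or subjects are added, and sample size, power and type I error are unaffected.
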